5.2 Eligibility (Inclusion/Exclusion) Criteria

Inclusion criteria for this study include:

- 1] Adult Malian males ≥ 18 years of age,
- 2] Uncomplicated malaria with $\geq 2,000$ asexual *P. falciparum* parasites per μl , and
- 3] Informed consent obtained and signed.

After obtaining the initial consent to treat, a physical examination and medical history will be obtained and recorded on a standard form. Thick smears will be obtained to diagnose *P. falciparum* infection. Patients who fulfill the first two criteria above will be invited to participate in the study, and informed consent will be obtained from those who choose to participate.

Exclusion criteria for this study include:

- 1] Severe or complicated malaria (including temperatures $\geq 40^\circ \text{C}$),
- 2] $\geq 100,000$ asexual parasites per μl of blood,
- 3] Anemia or other laboratory results (other than malaria) that require treatment (e.g., Hb ≤ 7 gm/dL, K $^+$ ≤ 3.5 mM, BP $\geq 140/90$),
- 4] Seizures or impaired consciousness,
- 5] Recent antimalarial treatment by history (within ≤ 2 weeks),
- 6] Chronic medications (including CYP3A4 inducers such as rifampin and nevirapine),
- 7] Ventricular or atrial arrhythmias including frequent ventricular premature beats or extrasystoles (> 20 per hour) or second or third degree heart block on the screening Holter recording,
- 8] Infection with other plasmodial species on the blood smear (*P. ovale*, *P. ovale*, *P. vivax*).

Enrollment and randomization will occur only after a final review to ensure that all of the inclusion criteria

have been met and that none of the exclusionary criteria are present.

6 STUDY PROCEDURES/EVALUATIONS

Table 1.

Study Schedule: PROOF OF CONCEPT EFFICACY STUDY OF AQ-13

Activity, Day(s) Tests Performed and Potential Findings

DIAGNOSIS, Day 1: Malian males ≥ 18 years with Fever and Chills	Blood smear to diagnose malaria in an adult Malian male is positive (and the subject fulfills none of the exclusion criteria)
INVITATION, Day 1: Invite to Participate in Study of AQ-13	Decide whether to participate in the Phase 2 Proof of Concept Study of AQ-13 by providing informed consent
SCREENING, Day 1: Subjects with malaria who provide consent	Screening 1 hour Holter recording, 2 tubes of blood for chemistry and hematology testing, eye examination
ENROLLMENT, Day 1: Randomize eligible, consented subjects	Randomization of subjects to AQ-13 (1596 mg orally over 3 days) or to the control arm, Coartem (4 tabs x 2/day x 3 days)
INPATIENT STUDIES: Days 1-7	Blood samples for drug and metabolite levels on days 1-5; Two tubes of blood for hematology and chemistry panels on day 4; 24 Holter recordings on dosing days 1-4; Urine collections on days 1-4; Eye exam plus an additional Holter recording at the end of week 1.
OUTPATIENT FOLLOW-UP, Days 8-42: (Weeks 2-6)	Five weeks of outpatient follow-up with 2 visits each week, to obtain 1 tube of blood for drug and metabolite levels on both visits in week 2, and 1 tube per week (at 1 of the 2 outpatient visits) in weeks 3 to 6; During week 2, there is a repeat 1 hour Holter recording and a review (discussion) of potential side effects (AEs).

6.1 Study Procedures

As noted above and in Flow Chart 4 below, the initial study procedures for subjects with uncomplicated *P. falciparum* malaria are a history and physical examination. The history and physical examination will be performed as outlined in the enclosed Case Report Form. Other study procedures that will be performed at the times of screening and enrollment include:

- Specimen Collection – performed by medical and nursing staff at designated times for collection of blood samples and 24 hour urines during inpatient days 1-4 (Flow Chart 4, page 26),
- Medical History – emphasizing fever, chills, other symptoms and signs of malaria, as well as weight loss and other signs of long-term and potentially confounding illnesses,
- History of concomitant Medications – emphasizing: a] medications for malaria in the past 2 weeks, and b] medications other than contraceptives, especially medications such as rifampin and nevirapine which induce 3A4 CYP450 activity and are therefore grounds for exclusion,
- Physical Examination – emphasizing conjunctival pallor (anemia), signs of increased cardiac output consistent with fever or anemia, splenomegaly (Hackett Classes I-V) [24],

- Counseling – other issues of concern to the patient.

6.2 Initial Laboratory Evaluation

Subjects thought to have uncomplicated *P. falciparum* malaria will be evaluated by obtaining a finger stick blood sample for a thick smear, filter paper blot and a rapid Hb determination in order to screen for *P. falciparum* malaria and anemia.

6.2.1 Laboratory Evaluations/Assays

Subjects who satisfy the first two inclusion criteria (adult Malian males \geq 18 years of age with uncomplicated *P. falciparum* malaria, and 2,000 to 99,999 asexual parasites per μl of blood) will be invited to participate in this study if they fulfill none of the exclusion criteria. Those who accept by providing their informed consent will have 2 additional tubes of blood drawn in Bamako for chemistry and hematology panels (1 each), including glucose-6-phosphate dehydrogenase (G6PD) assays and a separate sample for drug and metabolite blood levels that will also be used to freeze (cryopreserve) malaria parasites for future reference (Flow Chart 4, below on page 26). Laboratory evaluations or assays that will be performed in these studies include:

- Thick smear for asexual *P. falciparum* parasites with quantitative parasite counts (Mali; SOP)
- Filter paper blot for parasite and host genomic DNA (Mali; SOP)
- Rapid (Hemocue) Hb determination for anemia (Mali; SOP)
- Chemistry panel (Piccolo-Abaxis) (Mali; SOP)
- Hematology panel (Coulter A^{CT} 10) for Hb, Hct, WBC, platelets (Mali; SOP)
- Glucose-6-phosphate dehydrogenase (G6PD) determination (Mali; SOP)

6.2.2 Special Assays or Procedures

Prior to treatment with AQ-13 or Coartem, subjects will have a 1 hour baseline Holter recording to exclude pre-existing arrhythmias and other cardiac abnormalities and a baseline eye examination to ensure that there are no pre-existing ocular abnormalities before treatment or any new ocular abnormalities (potential AEs) after treatment. Randomization will be performed after the chemistry, hematology, eye and Holter recording results have been checked to ensure there are no criteria for exclusion and that informed consent to participate has been obtained and signed. Special assays or procedures that will be used in these studies include:

- PCR testing for parasite genotypes and for the K76T point mutation in *pfCRT* (Mali; SOP),
- Fluorescence HPLC assay for AQ-13 and its metabolites (New Orleans; SOP),
- Holter recordings for evidence of arrhythmias (Mali and New Orleans; SOP),
- Eye examinations pre- and post-treatment to test for evidence of keratopathy, retinopathy, other pre-existing abnormalities or treatment-related ocular side effects (adverse events) (Mali; SOP),
- Pharmacokinetic analysis of AQ-13 drug and metabolite blood and urine levels (Mali and New Orleans; SOPs for AQ-13 HPLC, CRFs for Out-Patient Follow-Up).

6.2.3 Specimen Collection, Preparation, Handling and Shipping

Blood Drawing for AQ-13 Drug and Metabolite Levels (Flow Chart, page 26, Section 7).

Because of the need to define the pharmacokinetics of AQ-13 and its metabolites, this blood sampling is more intense at the times of dosing (during days 1-3) when AQ-13 is being administered to the participants. (That is also the reason this table is below on a different page, because the substantial number of samples in Week One [n=25, Table 3, page 26] required that this table be presented in landscape orientation.)

After day 5, blood samples for the pharmacokinetic studies (drug and metabolite levels) will be drawn twice-weekly in the first week of outpatient follow-up (week 2 from day 8 to day 14) and once weekly during the subsequent 4 weeks (weeks 2 to 6 from days 15 to 42). The 25 samples obtained on days 1-5 plus the 10 samples obtained during outpatient follow-up are a total of 35 samples for the pharmacokinetic studies of AQ-13 and its metabolites at 5 ml apiece = 175 ml per subject.

6.2.3.1 Instructions for Specimen Preparation, Handling, and Storage

Specimens for chemistry, hematology and drug blood level testing are anticoagulated with lithium heparin, EDTA and CPD, respectively. Filter paper blots are kept in individually-labeled and dated envelopes in a dessicator at room or refrigerator temperature.

6.2.3.2 Specimen Shipments

Blood and urine specimens for the measurement of AQ-13 drug and metabolite levels will be shipped from Mali to Tulane University in New Orleans at 0-4° C because there have been no changes in those results when specimens have been stored at 0-4° C for ≥ 6 months. Specimens containing live frozen parasites shipped to New Orleans will be transported by commercial carrier using a CDC Permit for the Importation of Potentially Infectious Agents issued to the PI. Holter recordings will be sent from Bamako to New Orleans via the WEB using encryption to protect subject confidentiality, so they can be reviewed independently by cardiologists in both the U.S. and Mali using the *Box.com* WEB Site.

Permissible Concomitant Medications (Table 2, page 23, below)

As noted above, persons taking chronic medications and persons with chronic or acute diseases other than malaria will be excluded from participation in this study. However, in the course of uncomplicated malaria, supportive treatment is normally provided for: 1] fever and other discomforts, 2] nausea and vomiting, and 3] treatment of seizures (which would require withdrawal of the subject from this study for cerebral malaria). Therefore, those treatments (medications) will be allowed for participants in this study. Because the list provided below is based on discussions with Malian physician investigators, it focuses on drugs available in Mali, rather than drugs used for these indications in the U.S. For example, based on current practice in Mali, it lists: 1] paracetamol and aspirin including aspetic, rather than acetaminophen (Tylenol) for fever, headache, arthralgias and myalgias, and 2] metopimazine rather than prochlorperazine (Compazine) for nausea and vomiting.

Please note that: 1] these drugs and doses are not investigational (they are provided as examples of current practice for the supportive treatment of malaria in Mali) and 2] doses are provided only for adults because this study is restricted to adult Malian males ≥ 18 years of age with uncomplicated *P. falciparum* malaria.

Table 2.

Medications used for the supportive Care of Persons with Malaria in Mali

INDICATION	MEDICATION	DOSING
FEVER, DISCOMFORT		
Antipyretic Analgesics	Paracétamol Tablets 500 mg tablets	0.5-1.0 gm every 4-6 hours, not to exceed 4 doses per 24 hours,
	Paracétamol Injectable (Perfalgan), 10 mg/ml	Intravenous infusion of 1.0 gm (100 ml) not to exceed 4 doses per 24 hours,
	Aspirin Tablets	0.5-1.0 gm every 4-6 hrs, not to exceed 4 doses per 24 hours,
	Aspégic Injectable	1.0 gm every 6-8 hours, not to exceed 4 doses per 24 hours,
NAUSEA, VOMITING		
Antiemetics	Metopimazine (Volgalène) 5 and 10 mg oral, rectal	10 mg orally up to 3 doses per day, or 5-10 mg rectally not to exceed 3 doses/day
	Metopimazine Injectable	5-10 mg per injection, not to exceed 4 doses per day,
SEIZURES		
Anticonvulsants	Diazepam (Valium) 10 mg tablets	10-20 mg as needed, not to exceed 5 doses per 24 hours,
	Diazepam Injectable	10-20 mg as needed, not exceed 5 doses per 24 hours.

6.3 Screening

As noted above (section 6.2) and in Table 1, subjects thought to have uncomplicated *P. falciparum* malaria will be evaluated (diagnosed) by obtaining a finger stick blood sample for a thick smear, filter paper blot and a rapid Hb determination to screen for *P. falciparum* malaria and anemia. **The time between screening and enrollment must be ≤ 48 hours, although ≤ 24 hours is preferable** (intervals > 24 hours are acceptable if they result from consultation or deliberation related to informed consent). If a subject is eligible for the study and agrees to participate by providing their signed informed consent, other screening tests then performed will include a 1 hour Holter recording, 2 tubes of blood for chemistry and hematology testing and an eye examination (Table 1, Flow Chart 4).

6.4 Enrollment/Baseline, if applicable

Baseline data should be obtained within 24 hours of enrollment. This should allow for (permit) delays related to venipunctures for blood samples and the insertion of a heparin-lock to facilitate drawing multiple timed blood samples during the first 3 inpatient days, a 1 hour baseline Holter recording to exclude arrhythmias and a baseline eye examination.

6.5 Inpatient Period

Blood samples will be taken for drug and metabolite levels on days 1-5 and hematology and chemistry panels on day 4. After screening Holter recordings have been obtained and reviewed for pre-existing arrhythmias, continuous 24 hour Holter recordings will be performed on each of days 1-4 (focusing on the time between 2 and 6 hours after dosing for maximal effects on the QT interval). Urine collections will be performed on each of days 1-4. An eye exam plus an additional 1 hour Holter recording will be performed at the end of week 1.

6.6 Follow-up and Final Visits, if applicable

After completion of the 5-7 day inpatient stay (Flow Chart 4 below, and Table 1, above), there are 2 follow-up outpatient visits each week for the next 5 weeks (total of 6 weeks active involvement in the study). At each of the follow-up visits during Weeks 3-6, a blood sample is obtained for AQ-13 drug and metabolite blood levels to define the pharmacokinetics of AQ-13 and its metabolites. In addition, there is a final 1 hour Holter recording at the 2 week follow-up visit plus an in-depth interview about potential AEs.

Sequence of Events during the Follow-Up Outpatient Visits. The twice-weekly follow-up outpatient visits will include (in sequence): an interval history with discussion of potential AEs related to study drugs, review of current medications and a physical examination with recorded results for vital signs (blood pressure, heart rate, respiratory rate, temperature), conjunctival pallor, pulmonary, cardiac and abdominal examinations (including splenomegaly) (see the Out-Patient Follow-Up CRFs).

Allowable Windows (Times) for Follow-Up Outpatient Visits. The major purposes of the follow-up outpatient visits are to: 1] follow the pharmacokinetics of AQ-13 and its metabolites over time to estimate the terminal elimination $t_{1/2}$ and other pharmacokinetic parameters for AQ-13 and its metabolites in subjects with uncomplicated malaria and 2] to test for recurrent infection by distinguishing new infections (which do not represent recurrences or treatment failures) from recrudescences of infection with the same parasite genotypes (which do potentially represent treatment failures). Although the best data (in terms of points on the time-concentration curve to estimate the pharmacokinetic parameters) are provided by twice-weekly follow-up blood samples during the first two weeks (Weeks 1 and 2), the software that will be used for this purpose (PharSight) can adjust and still provide reasonable estimates of the relevant pharmacokinetic parameters no matter what the time points are. For this reason and because recurrent infection should be detected as soon as possible, late return visits will be permitted up to the final 6 week (42 day) time point.

6.7 Early Termination Visit, if applicable

Evidence for the recurrence of *P. falciparum* infection (positive smear for asexual parasites) at a follow-up outpatient visit within the 42 day period of post-treatment observation is reason for re-treatment and for the termination of a subject's participation in the study. At that time, blood will be drawn for AQ-13 drug and metabolite levels and to freeze asexual parasites for study in the future, 2 filter paper blots will be obtained, and repeat chemistry and hematology testing will be performed. The rationale for performing these studies at that time is to determine whether:

- a] **the recurring parasite was present at the time of the initial diagnosis and treatment** (in which case the recurrent infection would represent a treatment failure) and
- b] the blood levels of AQ-13 and its metabolites are within the expected range (in order **to exclude treatment failure due to ultrarapid metabolism of AQ-13** to its *N*-dealkylated metabolites by the CYP450 system).

6.8 Discontinuation or Withdrawal of a Subject

Treatment with AQ-13 or Coartem in this study may be discontinued for any of the reasons below. However, whenever possible (i.e., except when informed consent to participate has been withdrawn) subjects will be followed through to the conclusion of the treatment of their illness and outcomes will be examined using both *intent to treat* and *per protocol* analyses.

- 1] Recurrence of uncomplicated malaria,
- 2] Progression to severe or complicated malaria,
- 3] Development of ventricular tachyarrhythmias or conduction defects (new 2nd or 3rd degree heart block),
- 4] Other Serious Adverse Events (SAEs) possibly related to AQ-13, or
- 5] The subject's decision to withdraw his/her informed consent to participate.

If lack of cure (recurrence of uncomplicated malaria) occurs with either AQ-13 or Coartem, the subject will be treated with Quinine. Likewise, if a subject develops severe or complicated malaria, he will be treated with Quinine as recommended by the Mali Ministry of Health and the National Malaria Control Programme. Treatment with either AQ-13 or Coartem will be stopped in subjects who develop ventricular tachyarrhythmias, conduction defects or other serious adverse events (SAEs) possibly related to AQ-13 or Coartem. In those instances, further antimalarial treatment (if necessary) will be provided using Quinine based on the recommendations of the Mali Ministry of Health and the Mali National Malaria Control Programme.

Flow Chart 4.Work Sheet (schedule of procedures) for Phase 2 efficacy studies of AQ-13 in semi-immune Malian adult Males ≥ 18 years of age

Clinical	Scr	Pre-dose	0	30 m	1 hr	2	4	6	12	18	24	24:30	25	26	28	30	36	48	48:30	49	50	52	54	60	72	96	1/2 wks	
History/PE	X																										X	
Medication History	X																										X	
Assess for AEs		X							X										X						X		X ₁	
Laboratory																												
CBC,WBC, diff, plt	X																										X	
Chem 7	X																										X	
Liver profile	X																										X	
G6PD	X																											
AQ & Metabolites			X	X	X	X	X	X	X	X	X	X	X	X	X	X	X	X	X	X	X	X	X	X	X	X		
Freeze parasites			X																									
24 hr urine		X									X									X						X		
Diagnostics																												
Holter Recording	X		X ₂								X ₂								X ₂						X ₂		X ^{**}	
Eye exam	X																											X
Study Drug AQ-13 $\Sigma=1750$ mg			X ₃								X ₃								X ₃									
Coartem X ₄ =4 tabs			X ₄						X ₄		X ₄							X ₄	X ₄						X ₄			

X1 – To be performed by study Co-Investigator while inpatient and at follow-up

X2 – To be done over 96 hours (4 days), beginning at zero time on day 1

X3 – AQ-13 dose; to be given in the morning x 3 days.

X4 – Coartem dose (4 tablets in morning and afternoon x 3 days).

½ wks – at the end of week 1 and the end of week 2

* - blood draws at 96 and 120 hours after this, then twice a week for 6 weeks.

** - Holter recording for 1 hour at 1 and 2 week follow up visits.

Table 3.

WEEK ONE BLOOD SAMPLING SCHEDULE FOR AQ-13 DRUG AND METABOLITE LEVELS

Days	Day 1								Day 2								Day 3								4	5	6	
Hours	0	0.5	1	2	4	6	12	18	24	24.5	25	26	28	30	36	48	48.5	49	50	52	54	60	72	96	120			

Gantt Chart**ORGANIZATION OF THE PHASE 2 PROOF OF CONCEPT STUDY OF AQ-13**

	OUTPT	INPT	INPATIENT WEEK 1							OUTPATIENT FOLLOW-UP (WEEKS 2 TO 6)					
Recruitment	X	TESTS													
Informed Consent	X														
Thick Smear	X		X	X	X	X	X	X	X	2 per Week	2 per Week	2 per Week	2 per Week	2 per Week	2 per Week
Thin Smear	X														
Filter Paper Blot	X		X	X	X	X	X	X	X	2 per Week	2 per Week	2 per Week	2 per Week	2 per Week	2 per Week
Physical Exam	X		X	X	X	X	X	X	X	2 per Week	2 per Week	2 per Week	2 per Week	2 per Week	2 per Week
Hb	X						X								
Transport Decision	X														
Hematology Panel			X				X								
Chemistry Panel	X						X								
Eye Examination	X								X						
Holter (1 hour)	X								X	Day 14					
Holter (24 hours)			X	X	X	X									
Randomisation	X														
Drug Treatment			X	X	X										
Pharmacokinetics			8	6	7	1	1	1		2 per Week	1 per Week	1 per Week	1 per Week	1 per Week	
Parasite Clearance									X						
End of Inpatient Stay									X						
Completion of Study															Day 42
	OUTPT	INPT	INPATIENT WEEK ONE							OUTPATIENT FOLLOW-UP (WEEKS 2 TO 6)					
	TESTS	TESTS	1	2	3	4	5	6	7	8 to 14	15 to 21	22 to 28	29 to 35	36 to 42	
	DAYS									2	3	4	5	6	
	WEEK														

7 ASSESSMENT OF OUTCOME MEASURES

7.1 Specification of the Appropriate Outcome Measures

The major question being asked in these studies is whether AQ-13 is efficacious for the treatment of uncomplicated malaria due to *P. falciparum*. Therefore, the major outcome is whether treatment with AQ-13 clears *P. falciparum* parasites from the bloodstream and fever within 7 days without recrudescence within 42 days (3 times the 14-15 day terminal $t\frac{1}{2}$ of AQ-13 in human subjects) [11]. Because the transmission of malaria is often intense in Mali (100-300 bites per person per night during the rainy season), the data for recrudescence will be PCR-corrected [16-17]. Based on the amplification of selected polymorphic loci, recrudescences with parasites different from those in the initial infection will be categorized as new infections, which do not represent treatment failure. Conversely, recrudescences with parasites indistinguishable from those in the initial infection will be categorized as recurrent infections and do potentially represent treatment failures.

7.1.1 Primary Outcome Measures

Cure is a lack of recrudescence within 42 days (PCR-corrected) – no evidence of recrudescence with the same parasite genotype(s) after reduction of the asexual parasitemia to less than 25% of the admission value by day 3 and clearance of asexual parasites and fever by day 7. Failure is defined as “lack of cure”.

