QT	Interval from the beginning of ventricular depolarization (start of QRS) to the conclusion of repolarization (end of T wave)
QTc	QT interval adjusted (corrected) for heart rate
SAE	Serious Adverse Event
SOP	Standard Operating Procedure
t $\frac{1}{2}$	Half-Time (for concentration to decrease by 50%)
V_d	Volume of distribution (Liters)
WBC	White Blood Cell
WHO	World Health Organization
X	the percentage of the efficacy of the active control vs. placebo (C – P) that one desires to retain in the investigational drug (I) (see the Statistical Section on pages 37-40)

Title:	AQ-13 for Uncomplicated P. falciparum Malaria: Proof of Concept Study
Population:	Adult Malian males with uncomplicated Plasmodium falciparum Malaria This study will include adult Malian males ≥ 18 years of age in good general health (who have no known medical conditions other than malaria). Subjects who agree to participate and provide their informed consent will be randomized to one of two study arms (33 per arm \times 2 arms = 66 subjects) to receive either AQ-13 (1596 mg orally over 3 days) or Coartem (4 tabs twice daily \times 3 days).
Number of Sites:	There are several initial screening sites at: 1] the Missira/Sirakoroba Community Health Center in the Kolokani District and 2] referral outpatient clinics in and near Bamako. Although there is only one inpatient study site at the Clinical Research Center in Bamako, there will be two study follow-up sites for the 5 weeks of outpatient follow-up: the Community Health Center for Missira and Sirakoroba and the Clinical Research Center in Bamako.
Study Duration:	The duration of this study will be up to 15 months (including follow-up), beginning on June 15 th , 2013 and concluding on or before January 15, 2016.
Subject Duration:	The duration of each subject's participation will be 6 weeks, based on a 1 week inpatient stay for treatment/observation, plus 5 weeks of twice-weekly follow-up.

Primary Objective and Primary Endpoints:

1] The primary objective is to determine and compare the cure rates for AQ-13 and Coartem. Cure is a lack of recrudescence within 42 days (PCR-corrected) – no evidence of recrudescence with the same parasite genotype(s) after reduction of the asexual parasitemia to less than 25% of the admission value by day 3 and clearance of asexual parasites and fever by day 7. Failure is defined as lack of cure.

Secondary Objectives and associated Endpoints for comparisons of AQ-13 with Coartem:

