2.3 Potential Risks and Benefits

2.3.1 Potential Risks

Immediate (Short-Term) Risks. The first potential risk of participation in this study is that the investigational drug AQ-13 may not work; it may not cure uncomplicated *P. falciparum* malaria in Malian adults. If AQ-13 does not clear malaria parasites from subjects' blood by day 7 in the AQ-13 arm, those subjects will be treated with Quinine. In addition, if Coartem does not clear malaria parasites from subjects' blood in the Coartem control arm by day 7, these subjects will also be treated with Quinine, which is recommended in Mali for rescue in persons who fail treatment for uncomplicated malaria.

The most frequent side effects of AQ-13 in the volunteers who received it during the Phase 1 studies (and therefore the most likely adverse events (AEs) in these Proof of Concept studies) are similar to those of CQ: they include headache, dizziness, and digestive tract symptoms (nausea, loss of appetite, diarrhea, vomiting and abdominal pain). One of 126 subjects developed a mild, transient rash on her lower body, and 1 had muscle damage for several days, which is thought not to have been caused by the study drug, and is often caused by vigorous exercise. Other potential risks include bleeding, bruising, discomfort, black and blue spots and infection from venipunctures to obtain blood specimens. Abnormal beating of the heart is a potential risk, and has been observed in two subjects during the previous studies. Although it is thought not to have been caused by the study drug, the study drug will be stopped and subjects will be treated with quinine if they have abnormal beating of the heart and were randomized to AQ-13.

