8.2 Definition of a Serious Adverse Event (SAE)

An adverse event (AE) is serious and should be reported when the patient outcome is one or more of the following:

- Death,
- Life-threatening illness,
- Requires an inpatient hospitalization or the prolongation of an existing hospitalization,
- Results in persistent or permanent disability,
- Is associated with a congenital anomaly or birth defect,
- Requires intervention to prevent permanent impairment or damage. *Serious AEs do not include treatment failure with recurrent parasitemia and uncomplicated malaria (i.e., failure to clear asexual parasites from the bloodstream within 7 days or recurrence within 42 days).*

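### The cure definition does not say how to score a man given quinine early for severe malaria or a drug-stopping event, and both planned analyses can avoid counting him as a failure

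*Combined protocol and SAP*

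**What the plan says.** The synopsis, section 3 and section 7.1.1 all define cure by three conditions. Section 7.1.1 asks for no PCR-corrected recrudescence within 42 days "after reduction of the asexual parasitemia to less than 25% of the admission value by day 3 and clearance of asexual parasites and fever", with day 7 as the deadline for that clearance. Table 7 (section 10.1) lists the same components. Failure has no event list of its own; the synopsis says "Failure is defined as lack of cure". Section 8.2, when excluding treatment failure from serious adverse events, describes it as "failure to clear asexual parasites from the bloodstream within 7 days or recurrence within 42 days".

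Section 6.8 provides for quinine on two routes that can open before those conditions are assessed:

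- Severe malaria: "Likewise, if a subject develops severe or complicated malaria, he will be treated with Quinine".
- Ventricular tachyarrhythmia, conduction defect or another possibly related SAE, after which study drug stops: "In those instances, further antimalarial treatment (if necessary) will be provided using Quinine".

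The same section follows discontinued men where possible until treatment of the illness ends, and examines their outcomes by both ITT and per protocol. Section 10.3 bases ITT on the original randomization and limits per protocol to men who complete the protocol with complete information. Flow Chart 3 lists severe or complicated malaria as a withdrawal.

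**The concern.** Every part of the cure definition concerns parasites, fever or genotype. None refers to the treatment that produced the result. A man switched to quinine on day 2 could be below 25% of admission parasitemia by day 3, clear parasites and fever by day 7, and have no same-genotype recurrence. He would then satisfy the written definition.

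The scoring process would not necessarily catch this. Section 7.2.1 has blinded assessors score outcomes from the parasitologic data, and quinine use is not a stated input. Section 7.2.2 has progression to severe malaria judged separately, with no link to the primary endpoint.

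At stake is the non-inferiority claim. Crediting quinine's effect to AQ-13, or removing the man from the denominator, raises the AQ-13 cure rate. The temporary halting rule in Table 5 also counts failures: with 0 or 1 Coartem failures of 15, 3 AQ-13 failures prompt no action and 4 prompt a halt. One unscored rescue could matter there too.

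**Working it through.** **Which rescued men are affected**

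| Situation | Status under the written definition |
|---|---|
| Parasites or fever not cleared by day 7 | Failure already |
| Parasitemia not below 25% by day 3, rescued or not | Failure already |
| Same-genotype recrudescence by day 42 | Failure already |
| Severe malaria or drug-stopping event, early quinine, all targets then met | Not stated. Literal ITT: cure. Per protocol: may be excluded |

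Only the last row is open.

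**Inputs.** 33 per arm, Coartem cure 95%, margin 15 points, 80% power, 20% dropout (section 10.2); one-sided alpha 0.025, so a two-sided 95% interval (section 10.3). Equal cure in both arms for sample size is an assumption.

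**The plan's own figure.** n = 2 × 0.95 × 0.05 × (z + 0.842)² / 0.15². With z = 1.645 (one-sided 0.05), n = 26.1, and 26/0.8 = 32.5, giving Table 8's 26 and 33. With z = 1.960 (the stated 0.025), n = 33.1. Table 8 thus matches one-sided 0.05, which is a separate point. The checks below use the 95% interval of section 10.3.

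**Weight of one man.** 1/33 = 3.0 points; 1/28 = 3.6; 1/26 = 3.8.

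**Upper limit for C − E at n = 33**

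- Wald: U = (pC − pE) + 1.96 × √[pC(1−pC)/n + pE(1−pE)/n]
- Newcombe: U = (pC − pE) + √[(uC − pC)² + (pE − lE)²], where uC and lE are Wilson limits

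For 31 v 31, Wald is 0 + 1.96 × 0.0587 = 11.5 points. Newcombe is √(0.0438² + 0.1355²) = 14.2.

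For 31 v 30, Wald is 3.0 + 1.96 × 6.50 = 15.8 points. Newcombe is 3.0 + 15.1, which is 18.2 before rounding of the parts.

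| Cured, Coartem v AQ-13 | Wald | Newcombe |
|---|---|---|
| 31 v 31 | 11.5 | 14.2 |
| 31 v 30 (one AQ-13 man re-scored) | 15.8 | 18.2 |
| 32 v 32 | 8.3 | 12.5 |
| 32 v 31 (one AQ-13 man re-scored) | 13.1 | 16.8 |

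Starting from 31 v 31, one man reverses the conclusion by either method. Starting from 32 v 32, he reverses it only by Newcombe. If both true cure rates are 95%, moving one AQ-13 cure to failure reverses the conclusion in 23.9% of trials (Wald) or 25.8% (Newcombe), by exact binomial enumeration.

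**False non-inferiority.** The documents give no rescue rate, so the credited share is an assumption, shown as a range. Take Coartem cure as 95% and true unaided AQ-13 cure as 80%, exactly at the margin. If credited rescues add k points, the AQ-13 count is Binomial(33, 0.80 + k). Summing the probability of all outcomes with U < 15 points gives:

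| k (points) | Wald | Newcombe |
|---|---|---|
| 0 | 4.2% | 2.2% |
| 1.6 | 6.4% | 3.4% |
| 3 | 9.1% | 4.9% |
| 5 | 14.6% | 8.1% |
| 10 | 40.3% | 24.7% |

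The 1.6 is 2/126. Section 2.3.1 mentions two earlier subjects with abnormal heart beating and, separately, 126 subjects. Joining the two figures is itself an assumption, and the result serves only as a low anchor.

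**The case against.** The strongest reply is that the plan never says a rescued man is cured. Section 7.1 asks whether treatment with AQ-13 does the clearing. Section 2.3.1 describes quinine as rescue for men who fail treatment. Section 6.8 introduces severe malaria with a word that likens it to lack of cure. Section 7.2.2 has progression judged blind and compared by arm. Section 10.3 warns that dropping men who leave because of non-response inflates efficacy. This stands as evidence of intent, and a reader who inferred an explicit rule crediting rescue as cure would go beyond the text. But none of these passages sets a scoring rule, and the remedy in section 10.3 is only careful examination of the excluded men.

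Other limits also stand:

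- Follow-up under section 6.8 runs to the end of treatment of the illness, where possible. Day 42 is not promised, so a rescued man might lack the data for the last part of cure.
- No passage removes severe-malaria withdrawals from the ITT set.
- Sections 2.2 and 5.1 call the risk of severe malaria in these semi-immune adults extremely low.
- Counting a switch made purely for tolerability as an efficacy failure is a legitimate choice, but not the only one.

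Two further inferences are tempting and unsupported. One is to turn 2/126 into a 41% chance of an affected AQ-13 man: 1 − (1 − 2/126)^33 = 0.41. That is the chance of any abnormal heart beating, not of a mis-scored cure. Arrhythmias are screened out, quinine is given only if necessary, and section 2.3.1 says the events were thought not to be drug-caused. The other is to read "subjects will be treated with quinine if they have abnormal beating of the heart and were randomized to AQ-13" as proof that only AQ-13 men are exposed. That sentence sits in a risk narrative, while the stopping rule in section 6.8 covers both arms.

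**Conclusion.** The concern holds in a limited form. The scoring of men given quinine early is undefined. The literal ITT reading can credit quinine's effect to the study drug, and the per-protocol set may drop the man, so neither analysis need count him as a failure. Both lean toward non-inferiority.

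Few men should be affected, but one can decide a trial of this size. The 31 v 31 reversal is an illustration, and the 32 v 32 case shows that it does not always occur. The inflation of the false non-inferiority rate depends wholly on the assumed rescue share and on true AQ-13 cure lying at the margin. It is modest at 1.6 points (4.2% to 6.4% Wald, 2.2% to 3.4% Newcombe) and large only if early rescue is common.

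**What to change.** In the synopsis, section 3 and section 7.1.1, add to the cure definition that a subject is a treatment failure, in both the ITT and per-protocol analyses, if he progresses to severe or complicated malaria, or receives a non-study antimalarial for inadequate response before the cure criteria are assessed. State that men withdrawn for severe malaria stay in both analyses as failures. Re-treatment of a PCR-confirmed new infection keeps its present status under section 7.1.

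For switches made only for tolerability (arrhythmia, conduction defect, SAE), pre-specify one primary scoring, report these men on a separate line, and give a sensitivity analysis with the alternative scoring.

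Reconcile section 2.3.1, which mentions quinine after abnormal heart beating for men randomized to AQ-13, with section 6.8, which covers both arms.

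The cost is wording. No treatment changes and no new data are needed, since medications are reviewed at visits (section 6.6) and concomitant medications are reported on the CRFs (section 9.1). The reported cure rate may be slightly lower.
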